Subjects/Procedures: Subjects will be the same prodromal PD cohort described above in Aim 1. Subjects will continue the exercise intervention (or no intervention) for a total of 52 weeks to examine a potential disease-modifying effect. Subjects will continue to receive weekly phone calls from staff to monitor safety and compliance. At the end of the intervention period, control and exercise subjects will undergo repeat DaT SPECT with quantitation of signal in 6 different striatal regions (right and left caudate, right and left anterior putamen, right and left posterior putamen) and repeat exercise testing. If subjects choose to drop out, we will attempt to obtain the final DaT imaging study as soon as possible after notification of the subject's intent to withdraw if they have completed at least 24 weeks of the intervention.

AIM 3: To characterize the mechanism and biochemical correlates of exercise-induced changes in subjects with prodromal PD. In this aim, we will test the hypothesis that serum biomarkers of exercise effects and PD risk will change in the intervention group compared to no intervention.

Subjects/Procedures: Serum biomarkers associated with PD risk or exercise-induced changes (i.e. BDNF, uric acid and apolipoproteinA1) will be measured at baseline, 8 and 52 weeks as described above. The primary outcome of this aim will be differences in the rate of change between intervention groups as assessed using independent samples t-tests. A secondary outcome will examine the rate of change using linear mixed-effects models controlling for age, gender and other potential confounders. Additionally, relationships of biomarkers to VO2max, UPDRS, quantitative motor and quantitative DaT will be examined using partial correlations controlling for age and gender. An intention-to-treat analysis will be applied primarily but pre-planned secondary analyses will compare only exercise subjects deemed compliant with controls.

A schematic demonstrating the flow of recruitment, assessments and analysis is provided below:

[figure not shown]

Figure 3: Overview of study design

5.1.2. What research methods will be used in the project? *Check all that apply.*

 Surveys/Questionnaires	 Interviews	 Audio Taping
 Behavioral Observations	 Chart Reviews	 Video Taping

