5.5. Withdrawal of Subjects

5.5.1. Describe how a subject can withdraw from the study.

Subjects may withdraw from the study at any time by notifying study staff.

5.5.2. Describe any anticipated circumstances under which subjects will be withdrawn from the research without their consent.

Any subject who, in the opinion of the PI or co-investigators, has suffered significant injury or has demonstrated high risk for such may be withdrawn involuntarily

5.5.3. Describe the consequences of a subject's decision to withdraw from the research and the procedures for orderly termination of participation by the subject (e.g., the subject contacting the investigator for an end-of-study visit).

Early withdrawal from the study will not result in any consequences for the study subject. The subjects may inform the PI, co-PI, or research coordinator/assistant of their intention to withdraw in person or over the phone at any time. Subjects who wish to withdraw after completing at least 3 months of the study will be asked if they would be willing to complete a final study visit including DAT-SPECT but will be assured that this strictly voluntary as described in the Informed Consent Form.

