Aim 2: Because DaT SPECT signal loss is most sensitively detected in the putamen (particularly posterior putamen) in early PD, we will use this region to power our analysis. In our analysis of longitudinal DaT SPECT data from the PPMI study, average putamen signal was 0.83 (0.30) at baseline and 0.68 (0.23) at year 1 (absolute change 0.15 (0.13)), representing the expected change in the non-intervention group. With 35 subjects per group expected to complete the study (accounting for 20% drop-out), we are able to detect at least 0.06 points difference of change in average putamen signal between intervention and control groups (i.e., control group changes by 0.15 and intervention group changes by 0.09) with 80% power using two-sample t-test (alpha=0.05). As described in our preliminary data, the rate of rate of striatal degeneration during the prodromal period that we will capture may be greater than what been reported for the clinically manifest period of PD. Thus, the above estimates of the required sample size are conservative and it is likely that we could detect a significant effect of the intervention even if fewer than projected subjects complete the intervention (owing to greater attrition or decreased recruitment). For example if the non-intervention change in DaT uptake is 10% higher than we assumed (0.165 vs. 0.15), we could detect a similar effect size of the intervention with 29 (rather than 35) subjects per group. If the rate were 20% higher, we could detect a similar effect with 24 subjects. If the baseline rate of decline were 0.2 rather than 0.15 (33% higher), we could detect the effect with only 20 subjects per group.

Aim 3: One study has measured BDNF levels in PD patients before and after an 8 week exercise intervention(28). Baseline levels were mean (SD) 21 (3.4) and average post-intervention levels were 25(6.4) in the intervention group with no significant change in the non-intervention group. With 35 subjects per group expected to complete the study (accounting for 20% drop-out), we are able to detect a 4 point difference of change in BDNF between intervention and control groups using two-sample t-test with 80% power (alpha=0.05). This calculation assumes a conservative estimate of SD of change in the above calculation (SD=6.4, the largest SD of outcome in the above study).

9.2. Define plans for data and statistical analysis, including key elements of the statistical plan, stopping rules and endpoints.

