Aim 1: The primary outcome of this aim is comparison of the change in average UPDRS motor scores between the exercise and no intervention groups after 8 weeks. Between groups changes will be assessed with a two (independent) sample t-test. Secondarily, within group changes from baseline for UPDRS scores and quantitative assessments will be assessed using paired t-tests. Additionally, the relationship between change in fitness (Vo2max) and change in UPDRS scores will be assessed using partial correlations controlling for age, gender and baseline fitness levels. An intention-to-treat analysis will be applied primarily but pre-planned secondary analyses will compare only exercise subjects deemed compliant with controls.

Aim 2: The primary outcome of this aim is comparison of the change in semi-quantitative DaT uptake from scans at baseline and 52 weeks (post-intervention). Because DaT SPECT signal loss is most sensitively detected in the putamen (particularly posterior putamen) in early PD(69), we will focus the primary analysis on this region, though we will also examine signal changes in the caudate, anterior putamen and an index of right/left asymmetry. Differences in the rate of DaT signal change between groups will also be assessed using linear mixed-effects models which will allow us control for the influence of age, gender or other confounders. Linear mixed-effects modelling also accommodates the inclusion of data points with different follow-up times, allowing the analysis to include all subjects even if they do not complete the full intervention period. In this analysis, we will determine whether there is a significant effect of the “treatment group x time” interaction (rate of change) on the predictive value of models with DaT uptake as the dependent variable. An intention-to-treat analysis will be applied primarily but pre-planned secondary analyses will compare only exercise subjects deemed compliant with controls.

Aim 3: The primary outcome of this aim will be differences in the rate of change between intervention groups as assessed using independent samples t-tests. A secondary outcome will examine the rate of change using linear mixed-effects models controlling for age, gender and other potential confounders. Additionally, relationships of biomarkers to VO2max, UPDRS, quantitative motor and quantitative DaT will be examined using partial correlations controlling for age and gender.

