9.3. Provide sample size determination and analysis (include anticipated rate of screen failures, study discontinuations, lost to follow-up, etc.)

Based on power calculations, we anticipate screening 250 DIP subjects with olfactory testing, with the expectation that approximately 125 (50% of those screened) will be included in the imaging cohort, 88 (75% of those with abnormal olfactory testing) will be enrolled in exercise cohort and approximately 70 (assuming a 20% drop-out rate) will complete the study. 2018 Amendment: We anticipate enrolling 56 additional subjects under the modified inclusion criteria with 48 (24 per group) expected to complete all study activities. This will still allow for meaningful analysis of our primary outcomes according to the sensitivity analysis of sample size from the original protocol (20 per group adequate).

9.4. Describe how, where and by whom the data will be analyzed.

Preliminary statistical analyses will be conducted by the PI in the CMC PADRECC. Coded data will also be analyzed by [name], Associate Professor of Biostatistics at Penn and statistical advisor on [name] CDA award. [name] will have no access to the code that relates subjects' PHI to their study data

Section 10: References - Bibliography of cited literature

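### Aim 2 (and Aim 1): the primary comparison is not adjusted for the baseline value of its outcome; adding baseline DaT costs nothing and could remove up to about half the residual variance

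*Combined protocol and SAP*

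**What the plan says.** **Aim 2, analysis (section 9.2).** The primary outcome is a "comparison of the change in semi-quantitative DaT uptake from scans at baseline and 52 weeks", focused on the putamen. That sentence names no test. A linear mixed model follows as an additional analysis. It has DaT uptake as the response and allows control for age, gender or other confounders; baseline DaT is not named. In it, "we will determine whether there is a significant effect of the “treatment group x time” interaction (rate of change"), and the plan notes that the model "accommodates the inclusion of data points with different follow-up times".

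**Aim 2, sizing (section 9.1).** From PPMI data, "average putamen signal was 0.83 (0.30) at baseline and 0.68 (0.23) at year 1 (absolute change 0.15 (0.13")). With 35 completers per group, the plan claims to detect a difference in change of 0.06 "with 80% power using two-sample t-test (alpha=0.05").

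**2018 amendment (section 9.3).** A further 56 subjects are to be enrolled, "with 48 (24 per group) expected to complete all study activities".

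**Aim 1 (section 9.2).** The primary test is named: an independent-samples t-test on the 8-week change in UPDRS motor score. Baseline UPDRS is not a covariate.

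**The concern.** A t-test on change implicitly fixes the slope of the follow-up value on baseline at 1. When the true slope is below 1, the change score carries baseline noise that a regression on baseline would remove. The plan's own PPMI figures suggest this: the standard deviation falls from 0.30 to 0.23 over the year. The baseline scan is collected anyway, so the precision is given up for nothing. Aim 2 carries the disease-modification claim and expects only a few dozen completers per group, so the loss could matter there.

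**Working it through.** **Inputs (section 9.1, Aim 2).** SD at baseline 0.30, at year 1 0.23, of change 0.13; target difference 0.06; 35 per group; alpha 0.05. Sidedness is not stated, so two-sided is assumed. The amendment's 24 per group comes from section 9.3. Power uses the noncentral t with 2n−2 degrees of freedom for the t-test and 2n−3 for ANCOVA.

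**Step 1. The plan's own figure.** With SD 0.13 and 35 per group, the t-test has 48% power for 0.06. The difference detectable with 80% power is 0.088, and 0.06 would need 75 per group. The stated 0.06 needs an SD of about 0.088, so it does not reproduce from 0.13. That is a separate defect. It matters here only because it sets the true starting point at 48%.

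**Step 2. What baseline explains.** If the three SDs describe the same patients:

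- Covariance = (0.30² + 0.23² − 0.13²)/2 = (0.0900 + 0.0529 − 0.0169)/2 = 0.063
- Correlation = 0.063/(0.30 × 0.23) = 0.913
- Slope = 0.063/0.0900 = 0.70
- Residual variance given baseline = 0.0529 − 0.063²/0.0900 = 0.0088, SD 0.094
- Ratio to the change-score variance = 0.0088/0.0169 = 0.52, a 48% reduction

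Moving each SD within its rounding gives reductions from 39% (0.295, 0.235, 0.135) to 58% (0.305, 0.225, 0.125).

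**Step 3. Power for 0.06, same SDs in both arms, additive effect.**

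| | t-test on change | ANCOVA |
|---|---|---|
| Power, 35 per group | 48% | 75% |
| Power, 24 per group | 35% | 58% |
| Detectable at 80%, 35 per group | 0.088 | 0.064 |
| Detectable at 80%, 24 per group | 0.107 | 0.078 |
| n per group for 80% | 75 | 40 |

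Simulation with the slope estimated agrees: 48% against 74–75% at 35 per group, and 34% against 56–57% at 24.

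**Step 4. How far the gain depends on assumptions.**

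*Proportional effect.* Suppose exercise slows loss by 40% (0.15 to 0.09, as in the plan's example), with residual SD 0.094 in both arms.

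- Treated slope: 1 − 0.6 × 0.30 = 0.82
- Treated change variance: 0.18² × 0.09 + 0.0088 = 0.0117
- Average change variance: (0.0169 + 0.0117)/2 = 0.0143
- ANCOVA residual with a common slope of 0.76: 0.0088 + 0.06² × 0.09 = 0.0091
- Reduction: 1 − 0.0091/0.0143 = 36%
- Power: about 54% to 74% at 35 per group, and 40% to 57% at 24

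*Different paired year-1 SD* (0.30 and 0.13 held):

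| Year-1 SD | Variance reduction | ANCOVA power, 35 per group | ANCOVA power, 24 per group |
|---|---|---|---|
| 0.25 | 32% | 64% | 48% |
| 0.27 | 19% | 56% | 41% |
| 0.30 | 5% | 50% | 36% |

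**Step 5. Does the mixed model already do this?** With both scans complete, DaT as the response and a free group term, the group-by-time estimate is the difference in mean change. In one simulated data set both analyses gave an estimate of 0.0505 with standard error 0.0303. The model would draw on baseline for precision only if baseline means were constrained equal across arms, which the plan does not state.

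**The case against.** **The primary test is not really missing.** A reader might infer from section 9.2 that Aim 2 has no identifiable primary test. The documents do not support that. Section 9.1 sizes Aim 2 on a two-sample t-test, 9.2 presents the mixed model as additional, and Aim 3 ranks the same two methods in that order. The t-test is readily inferred; what is absent is the covariate.

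**The planned test is valid.** This stands. Randomisation protects the change-score comparison, so nothing here amounts to bias or error.

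**The headline gain is near the favourable end.** This largely stands. The 48% depends on the SD falling from 0.30 to 0.23 in the same patients, which 9.1 does not confirm. It also depends on PPMI patients resembling this cohort and on the change SD applying to the exercise arm, although 9.1 offers the PPMI change as the expectation for the non-intervention group. The gain shrinks under the alternatives in step 4, but in none of them does adjustment do harm.

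**The reference to other confounders could cover baseline DaT.** It leaves room for it but does not name it, and it applies to the additional model only.

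**Twenty-four per group may not be the analysed number.** The amendment speaks of additional subjects, and the documents do not say whether their 24 completers per group add to earlier ones. The 24-per-group figures hold only if 24 is the total.

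**Aim 1 is different.** It names its test, so it shares only the missing covariate.

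**Conclusion.** The point holds as a free improvement in precision for Aim 2. With paired PPMI SDs that carry over, the same change SD in both arms and an additive effect, adjusting for baseline DaT removes about 48% of the change-score variance (39–58% from rounding). The cut is about 36% under proportional slowing of 40%, and 32%, 19% or 5% if the paired year-1 SD is 0.25, 0.27 or 0.30. The gain is therefore up to about half, not a promised half.

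A reader might also infer that adjustment rescues the Aim 2 power claim. It does not: even in the favourable case power is 75% at 35 per group, and 40 per group would be needed for 80%.

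For Aim 1 the gain is probably smaller. The documents give no baseline SD, follow-up SD or correlation for UPDRS, so it cannot be computed from them.

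**What to change.** - **Aim 2, section 9.2:** name as primary an ANCOVA of 52-week putamen DaT on randomised group and baseline putamen DaT. Keep the change-score t-test as supportive, and the mixed model as the additional analysis for unequal follow-up.
- **Aim 2, section 9.1:** restate power under the ANCOVA for the number of completers actually expected per group. State the SDs used, whether they are paired, and whether the amendment's 24 per group is the total.
- **Aim 1, section 9.2:** replace the change-score t-test with an ANCOVA of the 8-week UPDRS motor score on group and baseline score.

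The cost is a few sentences of analysis-plan wording, one restated power figure and one degree of freedom per model. No new data or visits are needed. The change should be made before outcome data are compared by arm.

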DVR Determination: Quantification of SPECT dopamine transporter is determined using distribution volume ratios, DVR's. Essentially, a DVR can be thought of as a punch biopsy of neuroanatomical location. In keeping with previously published TRODAT imaging analysis, average counts per millimeter cubed will be obtained for seven volumes of interest (VOIs), the same obtained from each data set in prior publications: [1] Right Caudate Nucleus (RC), [2] Left Caudate Nucleus (LC), [3] Right Anterior Putamen (RAP), [4] Left Anterior Putamen (LAP), [5] Right Posterior Putamen (RPP), [6] Left Posterior Putamen (LPP) and a cortical background value (Right Superior Parietal Lobule, RSPL). Cerebellar VOIs may also be used in keeping with prior studies. Both cortex superior to the level of the basal ganglia and cerebellum are appropriate as reference regions as they have very low concentrations of DAT. VOIs will be determined using in-house developed software based on the Siemens platform. VOIs will be defined using the corresponding low dose CT images for anatomical localization. Mean distribution volume ratios (DVR's) will be calculated of each striatum VOI relative to cortical background using the following formula : $DVR = (VOI - \text{Reference Region}) / \text{Reference Region}$. For

comparison, Similar ROIs will be quantified using DaT-quant automated analysis (GE Healthcare) and MIMNeuro (MIM Software).

All subjects receiving I-123 Datscan will be older than 18, as our inclusion criteria specify recruiting only subjects 40 years and older. Each dose administered to subjects will be recorded as part of the CRF and any doses previously received by subjects recruited from [name] CPPF pilot protocol will also be documented. For subjects recruited from the CPPF protocol, we anticipate that their scan from the pilot protocol will also serve as their baseline scan for the present study. If more than 3 months have elapsed since the pilot study scan, subjects will be asked to complete a new baseline scan for the present study as well as the post-intervention phase scan 12 months later (3 scans over 15 or more months).

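### Aim 2's primary DaT endpoint is not tied to one variable: power is set on average putamen, while the analysis section stresses posterior putamen and lists anterior putamen separately

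*Combined protocol and SAP*

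**What the plan says.** **Power (Section 9.1, Aim 2).** The section names the putamen, especially the posterior part, as the powering region. The figures that follow are for the average: "average putamen signal was 0.83 (0.30) at baseline and 0.68 (0.23) at year 1", with a one-year change of 0.15 (SD 0.13). The conclusion is that "we are able to detect at least 0.06 points difference of change in average putamen signal between intervention and control groups", with 35 completers per group.

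**Analysis (Section 9.2, Aim 2).** The primary outcome is the change in semi-quantitative DaT uptake from baseline to 52 weeks. The section repeats the emphasis on posterior putamen and continues: "we will focus the primary analysis on this region, though we will also examine signal changes in the caudate, anterior putamen", together with an index of asymmetry.

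**Quantification (Section 5.1.1, DVR Determination).** Anterior and posterior putamen are separate volumes of interest (VOIs) on each side. The DVR is calculated against cortical background (right superior parietal lobule, RSPL), with VOIs set by in-house software. The section adds: "Cerebellar VOIs may also be used in keeping with prior studies". DaT-quant and MIMNeuro are introduced as a comparison.

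No section says how the two sides or the two putamen subregions form one primary value. No multiplicity adjustment is described.

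**The concern.** A programmer given only this text could not derive a single primary variable. If anterior putamen is an additional region, the primary is posterior putamen, and the power figures belong to another measure. If the whole putamen is primary, anterior putamen is both inside the primary and listed apart from it. The optional cerebellar reference adds a second open point.

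At stake is the disease-modification claim (Hypothesis 2). If the variable is settled only after the data are seen, the nominal 5% error rate no longer holds. Two features make advance definition more important. Section 5.1.1 blinds the initial visual reader to clinical status, but no section says that VOI quantification is blinded to arm. Section 9.4 has the principal investigator run preliminary analyses.

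**Working it through.** **1. The plan's own power figure.** Inputs from Section 9.1, Aim 2: difference 0.06 (0.15 against 0.09), SD of change 0.13, 35 per group, alpha 0.05 (taken as two-sided), two-sample t-test.

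- Standardised difference: 0.06 / 0.13 = 0.46.
- Power, normal approximation: Φ(0.46 × √(35/2) − 1.96) = Φ(1.93 − 1.96) = 49%. The noncentral t gives 48%; one-sided, about 61%.
- Detectable difference at 80% power: 0.679 × 0.13 = 0.088.
- Sample size for 0.06: 2 × (1.96 + 0.84)² × (0.13/0.06)² ≈ 74 per group (75 by the t-test).
- SD that would make 0.06 detectable with 35 per group: 0.06 / 0.679 = 0.088.
- At 24 per group (2018 amendment, Section 9.3): detectable difference 0.107; power for 0.06 is 35%.

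The stated 0.06 at 80% power is therefore not reproduced, even for average putamen. For posterior putamen no power can be computed, because the documents give no mean or SD of change for it.

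**2. How many candidate measures the text supports.**

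- Region: average putamen (9.1) or posterior putamen (the literal reading of 9.2) gives 2.
- Reference: cortical default or optional cerebellum gives a further factor of 2, so 4 in all.
- Software: in-house is the stated method and the other two packages are for comparison, so nothing is added.

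**3. Type I error if the best of k measures could be reported.** Under the null, k z statistics with common correlation ρ are drawn as X_j = √ρ·Z₀ + √(1−ρ)·Z_j. A false positive is max|X_j| > 1.96. One million draws per setting:

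| k | ρ = 0.95 | 0.9 | 0.8 | 0.7 | Independent, 1 − 0.95^k |
|---|---|---|---|---|---|
| 2 | 6.5% | 7.0% | 7.8% | 8.4% | 9.8% |
| 4 | 8.0% | 9.4% | 11.4% | 13.1% | 18.5% |

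The correlations are assumptions. One pointer for k = 2 is that posterior putamen is part of average putamen. With equal SDs, the correlation of part with whole is √((1 + r)/2), where r is the anterior-posterior correlation. For r = 0.5 to 0.8 (also assumed) this is 0.87 to 0.95, and type I error is about 6.5-7.3%. A correlation near 0.7 would need r near 0.

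**The case against.** The best defence is that Sections 9.1 and 9.2 use the same description of the region. On that view whole putamen is primary, and anterior putamen, caudate and asymmetry are further looks. The reading is coherent, so it would go too far to infer that the two sections flatly contradict each other, or that 9.2 declares posterior putamen primary and anterior putamen secondary. But 9.2 does not state the whole-putamen reading either, and setting one putamen subregion apart from the primary focus points the other way.

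Other stronger inferences are also unsupported:

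- **Software left open.** A reader might count three packages and reach 12 candidate measures (10.4-23.3% over the same correlations). Section 5.1.1 names the in-house method and offers the others for comparison, so that count falls away. What remains is that 9.2 does not tie the primary analysis to the in-house method.
- **Reference region left open.** The DVR formula uses cortical background. Only the cerebellar option lacks a rule.
- **The plan intends to choose the best result.** Nothing says so; 9.2 separates a primary focus from additional regions. The error rates show what the wording permits.
- **Average putamen is adequately powered, so choosing it solves the problem.** Step 1 of the working shows otherwise.

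It is also fair to say that 9.1 does not describe how its average putamen figure was formed, or with which reference and software. No summary can be shown to match it exactly.

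**Conclusion.** The concern stands as an ambiguity in a primary endpoint that should be resolved. The power section and the literal reading of the analysis section point to different variables, and nothing says how VOIs and sides combine. The supported room for choice is two measures, or four with the cerebellar option. The corresponding type I error is about 6.5-8.4% or about 8-13%, if the better result could be selected and correlations lie between 0.95 and 0.7. The part-whole relation favours the lower end for two measures. The inflation is moderate and a default pipeline exists. Separately, the 80% power statement fails on its own inputs for average putamen (about 48% at 35 per group, about 35% at 24) and cannot be assessed for posterior putamen.

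**What to change.** Before any scan data are compared by arm, name one primary variable in Section 9.2. An example is the 52-week change in mean DVR over the four putamen VOIs (anterior and posterior, both sides), with the cortical (RSPL) reference and the in-house VOI method, processed identically at both scans. Identical processing matters because Section 5.1.1 allows some baseline scans to come from the pilot protocol.

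Label posterior putamen alone, anterior putamen, caudate, asymmetry, the cerebellar reference, DaT-quant and MIMNeuro as secondary or sensitivity analyses.

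If posterior putamen is preferred as primary, state power with that region's own SD of change. In either case, replace the 80% figure with one recomputed from the chosen variable's SD and the expected number of completers.

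The cost is wording and a recalculation, with no new data, visits or participants. The downside is losing the freedom to switch region or reference later.

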5.1. Study Design

5.1.1. Describe in detail the experimental design, i.e. from recruitment procedures to study closure.

Subjects: Patients aged 40-89 with a clinical diagnosis of DIP or PD will be recruited from the PVAMC PADRECC and Behavioral Health Service (BHS) clinics.

Inclusion criteria: We will recruit subjects with parkinsonian signs (rest tremor, rigidity, bradykinesia) occurring after the institution of therapy with a medication having a known association with DIP (examples include haloperidol, chlorpromazine, fluphenazine, perphenazine, risperidone, thioridazine, thiothixene, lithium, valproic acid, ziprasidone, olanzapine and aripiprazole). Potential subjects with DIP will be pre-screened using a brief (12 item) scratch and sniff smell test with hyposmic subjects invited to learn more about the study (see script). Brief olfactory testing should be completed in 5-10 minutes. We will also invite subjects from [name] CPPF pilot study "Degenerative nigrostriatal dysfunction in drug-induced parkinsonism" PROM#01481 who have abnormal DaT-SPECT to enroll in the present protocol. These subjects will have explicitly agreed to future contact for related studies in the ICF for PROM#01481. We may also invite subjects identified by their PADRECC provider who had DaT-SPECT (with an abnormal result) performed clinically outside of a research protocol within the prior 3 months and agree to be contacted. We will also recruit subjects with a clinical diagnosis of PD (Hoehn & Yahr (H/Y) stage ≤ 2 made by a PADRECC provider.

Exclusion criteria: 1) Subjects with a known diagnosis of, atypical parkinsonian syndromes (i.e. dementia with Lewy bodies, progressive supranuclear palsy, corticobasal degeneration, multiple system atrophy) or other neurodegenerative condition, with the exception of PD, will be excluded; 2) Subjects with a history of sinus trauma or surgery, encephalitis, current nasal congestion or other known reason for olfactory impairment will not be screened 3) Subjects with a contraindication to DaTl (sensitivity or allergy to iodine, treatment with a drug with a significant effect on DaTscan that cannot be temporarily weaned)

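### In Aim 2's additional mixed model, weeks before randomisation would count as time on assignment when an earlier scan is the baseline, which dilutes the estimated difference in rate of DaT decline

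*Combined protocol and SAP*

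**What the plan says.** **Baseline scan.** For subjects coming from the pilot protocol, Section 5.1.1 (DVR Determination) says "we anticipate that their scan from the pilot protocol will also serve as their baseline scan for the present study". It adds: "If more than 3 months have elapsed since the pilot study scan, subjects will be asked to complete a new baseline scan". The date from which the 3 months are counted (consent, enrolment or randomisation) is not stated. Section 5.1.1 also admits subjects "who had DaT-SPECT (with an abnormal result) performed clinically outside of a research protocol within the prior 3 months"; that such a clinical scan would be the study baseline is implied, not written.

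**Final scan.** Section 5.1.1, Aim 2: "At the end of the intervention period, control and exercise subjects will undergo repeat DaT SPECT". The intervention lasts 52 weeks. For withdrawals, Section 5.1.1 seeks an early final scan after at least 24 weeks of intervention, whereas Section 5.5.3 asks for one after at least 3 months of study.

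**Analysis.** Section 9.2, Aim 2: "The primary outcome of this aim is comparison of the change in semi-quantitative DaT uptake from scans at baseline and 52 weeks (post-intervention". The rate is an additional analysis: "Differences in the rate of DaT signal change between groups will also be assessed using linear mixed-effects models". On the interaction, the text reads "we will determine whether there is a significant effect of the “treatment group x time” interaction (rate of change". The model is justified partly because "Linear mixed-effects modelling also accommodates the inclusion of data points with different follow-up times". Neither the origin nor the coding of time is defined, and no term is given for the interval between baseline scan and randomisation.

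**The concern.** A subject who enters with a 3-month-old scan and completes the trial has about 15 months between scans, of which 12 follow randomisation. With two scans, the subject's slope is the change divided by the interval. Exercise can slow decline only after randomisation, yet all 15 months are in the denominator. The interaction is then an average over assigned and unassigned time, and it understates the slowing attributable to exercise.

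At stake is the size of the effect in the analysis that addresses Hypothesis 2 (slower decline) as a rate, and that is meant to bring in subjects who stop early. Nothing in the model output would reveal the dilution.

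**Working it through.** **Inputs.** Section 9.1, Aim 2: control change 0.15 over one year (SD of change 0.13); exercise change 0.09; 35 completers per group. Section 5.1.1: lag up to 3 months (13 weeks), intervention 52 weeks, early scan from 24 weeks. Section 5.5.3: early scan from 3 months. Assumptions: both arms decline at 0.15 per year before randomisation, and the exercise effect accrues linearly after it.

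**The plan's own figures.** The target difference is 0.15 − 0.09 = 0.06, a slowing of 0.06/0.15 = 40%. The claim of 80% power with 35 per group does not reproduce with SD 0.13: n = 2 × (1.96 + 0.84)² × 0.13²/0.06² gives 74 per group, and power at 35 is about 48%. That is a separate matter and the present point does not depend on it.

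**One subject.** Let L be the lag and T the time on assignment, in years.
- Exercise slope = (0.15L + 0.09T)/(L + T); control slope = 0.15.
- Difference = 0.06 × T/(L + T).

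| Final scan | Lag | T/(L + T) | Difference per year | Dilution |
|---|---|---|---|---|
| 52 weeks | none | 1.00 | 0.060 | 0% |
| 52 weeks | 1 month | 12/13 = 0.92 | 0.055 | 8% |
| 52 weeks | 3 months | 12/15 = 0.80 | 0.048 | 20% |
| 24 weeks | 13 weeks | 24/37 = 0.65 | 0.039 | 35% |
| 3 months | 3 months | 3/6 = 0.50 | 0.030 | 50% |

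In the third row the exercise slope is (0.0375 + 0.09)/1.25 = 0.102, so a 40% slowing appears as 0.048/0.15 = 32%.

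**Coding of time.** Setting time zero at randomisation and giving the baseline scan a negative time leaves the slope between the two scans unchanged. Nominal coding (0 and 52 weeks) removes the dilution for completers, but it does not use the actual follow-up times that early scans need.

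**Whole trial.** Suppose a share s of subjects has the full 3-month lag and all complete. A random-intercept model with two scans weights slopes by the interval squared, so the fraction recovered is (1 + 0.25s)/(1 + 0.5625s).

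| s (assumed) | Recovered | Dilution |
|---|---|---|
| 10% | 1.025/1.05625 = 0.970 | 3% |
| 25% | 1.0625/1.140625 = 0.931 | 7% |
| 50% | 1.125/1.28125 = 0.878 | 12% |
| 100% | 1.25/1.5625 = 0.800 | 20% |

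Simulation with 35 per arm and SD of change 0.13 agrees to within about a percentage point (12 to 13% at a share of 50%).

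**Primary comparison of change.** For completers with a 3-month lag, control change is 0.15 × 1.25 = 0.1875 and exercise change is 0.0375 + 0.09 = 0.1275. The difference is 0.060, undiluted.

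**Power.** The standard error of the difference in change is 0.13 × √(2/35) = 0.031. If the SD of change does not grow with the interval and everyone has the 3-month lag, the rate's standard error also shrinks by 12/15: 0.048/(0.031 × 0.8) equals 0.060/0.031, so the test is the same. If instead the SD of the rate stays at 0.13, power falls from 48% to 33%. That loss comes from the noisier change: 0.060/(0.13 × 1.25) equals 0.048/0.13, so recoding time would not recover it.

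**Proposed model.** In the same simulations, a common slope in time since the baseline scan plus treatment by time since randomisation returned 0.060 at every share.

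**The case against.** The strongest reply is that little rests on this model. The primary outcome is the change between scans, Section 9.1 powers Aim 2 on a two-sample t-test, and the rate is assessed in addition. The interaction is described as a significance test, and under no effect there is no bias. Even the worst completer case, 0.012, is about 0.4 of the 0.031 standard error. Most subjects may have no material lag: Sections 5.1.3 and 9.3 derive the 88 randomised from the trial's own screening, pilot and clinical-scan subjects are additional, and the radiation-dose text in Section 5.1.1 expects nearly all subjects to have two scans about 12 months apart.

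Most of that stands, and it rules out several stronger readings that a reader might infer:
- *The trial's result is understated by 20%.* The documents give no share of lagged subjects; 20% needs all of them to have the full lag.
- *20% is a ceiling.* It is not. Early exit scans exceed it, and the 3-month limit is not tied to randomisation.
- *The primary Aim 2 comparison is biased.* It is not, for completers scanned at the end of 52 weeks.
- *The plan prescribes the full scan-to-scan interval.* It leaves time undefined; actual time is an inference from its reference to differing follow-up.

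In-trial scans also precede safety screening, fitness testing and randomisation with no stated limit, but the documents give no delay from which to draw a bias.

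What the reply does not answer is that the model is offered as the way to use unequal follow-up, that this calls for actual times, and that actual times with a single interaction give a diluted coefficient for any lagged subject. The dose text does not settle it either. If the final scan fell 12 months after a 3-month-old baseline, only 9 of 12 months would follow randomisation; the dilution would be 25% and the change comparison would shrink to 0.045.

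**Conclusion.** The point holds for Aim 2's additional mixed model. Fitted with actual scan times and one treatment-by-time term, it is biased toward no effect for subjects whose baseline scan predates randomisation: 20% for a 52-week completer with a full 3-month lag, 35% for a 24-week exit scan with that lag, and 50% for a 3-month one. At trial level the range among completers is about 3% to 20% for assumed shares of 10% to 100% with the full lag; the true share is not given.

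These sizes assume equal decline in both arms before randomisation and a linear exercise effect after it. Section 5.1.1 describes exercise building up to target, so the second assumption is a simplification. The effect is on the reported size of slowing; power is essentially unchanged if the SD of change does not grow with the interval. The matter is worth correcting but does not threaten the primary comparison.

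**What to change.** In Section 9.2, Aim 2, mixed model only:
- Use actual dates and enter two time terms: time since the baseline scan, as decline common to both arms, and treatment group by time since randomisation, set to 0 at the baseline scan.
- Report the second coefficient as the difference per 52 weeks of assigned intervention.
- State the date from which the 3-month limit on prior scans is counted, and whether clinical scans serve as baseline.

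The primary comparison of change needs no lag covariate, since the lag does not bias it. Separately, Sections 5.1.1 and 5.5.3 give different thresholds for the early final scan (24 weeks and 3 months) and must be reconciled.

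**Cost.** Wording only; no new visits, scans or subjects. Scan and randomisation dates must be in the analysis file, which the documents do not explicitly confirm. The model also assumes equal pre-randomisation decline in the two arms, which randomisation supports.
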